## PROTOCOL SYNOPSIS

TITLE	Phase II Trial of Organ Preservation Program Using Short-Course Radiation and FOLFOXIRI for Rectal Cancer (SHORT-FOX)
STUDY PHASE	Phase II
INDICATION	Treatment
INVESTIGATIONAL PRODUCT OR PROCEDURE	Organ preservation approach using short course radiation followed by FOLFOXIRI for patients with non-metastatic, >T2N0 or low T2N0 rectal cancer
PRIMARY OBJECTIVE	To assess clinical complete response of an organ preservation approach using short course radiation followed by intensified chemotherapy
SECONDARY OBJECTIVES	To assess safety in all enrolled patients, local regrowth rate and other cancer specific outcomes (disease-free survival, colostomy-free survival and overall survival), longitudinal health-related quality of life of this organ preservation approach
TREATMENT SUMMARY	Patients will undergo short-course radiation followed by 4 months of FOLFOXIRI. Those who achieve a clinical complete response will be considered for organ preservation approach. All other patients will receive standard of care total mesorectal excision (TME).
SAMPLE SIZE	37 patients
STATISTICAL CONSIDERATIONS	
Sample Size Calculation: We plan to use an optimal Simon 2 stage design and enroll 37 patients with an interim analysis at 17 patients for futility.
 
Primary Endpoint: Clinical complete response assessed 8 (+/-4) weeks after completion of chemotherapy.
 
Secondary Endpoints: Toxicity, local regrowth rate, disease-free survival, colostomy-free survival, and overall survival assessed until study completion.
 
Exploratory Endpoint: Health-related quality of life assessed until study completion.

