### **4.2 Treatment Schedule**

Study treatment will start within 30 days of eligibility determination.

Treatment will comprise 6 daily fractions of RT at 5 Gy per fraction followed 2-4 weeks later by approximately 4 months of chemotherapy.

Patients will be assessed for the primary outcome approximately 8 weeks (+/- 4 weeks) following completion of chemotherapy. Those who are not eligible for organ preservation will proceed with TME. All others will undergo organ preservation and surveillance for local regrowth for 2 years on protocol.

Treatment will be administered on an outpatient basis. No investigational or commercial agents or therapies other than those described may be administered with the intent to treat the patient's malignancy.

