#### **4.2.5 Follow-Up Schedule (Time 0 = assessment of primary outcome)**

Patients who achieve cCR and are candidates for organ preservation per multidisciplinary review will undergo surveillance per protocol schedule. If tumor shows near complete response, patient may continue to be observed until the next evaluable timepoint.

Additional scans and/or other tests may be performed and will be based on the clinical judgment of the treating physician.

Patients who are not candidates for organ preservation will proceed with TME. These patients will not proceed with the organ preservation surveillance schedule and instead be followed for cancer-specific outcomes (disease-free survival, colostomy-free survival and overall survival) per standard of care as directed by the treating physician. They will be assessed for AEs and health-related quality of life per Study Calendar.

For patients who achieve cCR and are on surveillance schedule, if suspicion of local regrowth (non-resolving residual abnormality that appears to increase in size or appears more suspicious in appearance or palpation, or imaging characteristics concerning for progression), patient will undergo a biopsy or a transanal full-thickness excision (TAE) if deemed appropriate to confirm. If biopsy is positive, patients will be managed per standard of care as directed by the treating physician.

Patients who pursue treatment for disease progression while on study will continue to be followed for OS, but discontinue routine AE assessment and QOLs, and follow-up with their treating physicians per standard of care.

After 2 years, all patients who initiated treatment on the protocol will be off study and followed for survival only. In general, patients who opt for organ preservation are recommended to continue to undergo surveillance years 3-5 as per below:

Recommend surveillance off study during years 3-5:

- Every 3-6 months
  - Exam and sigmoidoscopy
- Every 6 months
  - MRI pelvis and CT chest every 6 months

Follow-up PET/CTs or PET/MRI (preferred) are optional at any follow-up point, as per treating physician.

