### 10.2 Secondary Outcome Measures

- Toxicity at least possibly attributed to treatment, graded using CTCAE v5 criteria and assessed up to 3 months after completion of RT and chemotherapy, expressed as a number and proportion without dispersion.
- 2-year local regrowth rate where local regrowth is defined as the presence of adenocarcinoma within the rectal wall or within the mesorectum confirmed by pathology, expressed as a percentage with its 95% confidence interval.
- DFS defined as the time from the start date of RT to the date of the first documented progression or death due to any cause assessed up to 2 years after completion of chemotherapy. Patients will be censored at the last date of follow-up if lost to follow-up prior to two years, expressed as a median with interquartile range.
- Colostomy-free survival defined as the time from the start date of RT to the date of colostomy or death due to any cause assessed up to 2 years after completion of

chemotherapy, expressed as a median with interquartile range. Patients will be censored at the last date of follow-up if lost to follow-up prior to two years.

- OS defined as death from any cause from start date of RT until death, study completion, or loss to follow-up, whichever occurs first. This will be reported as median survival time with interquartile range.

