### **12.5 Secondary Analysis**

#### **12.5.1 Analysis Population**

For the secondary outcome of local regrowth rate, the analysis population will include all patients managed with organ preservation approach. For the secondary outcomes of

toxicity, DFS, colostomy-free survival, OS and HRQOL, the analysis population will be the same set of patients included for the primary analysis.

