### **12.5.2 Analysis Plan**

For the toxicity outcome, we will calculate the proportion of patients meeting our definition of toxicity. In addition, we will present the frequency and percent of other adverse events reported in the study.

Local regrowth rate will be calculated as the proportion of patients with local regrowth based on the secondary analysis population. The local regrowth rate and its 95% confidence interval will be calculated.

Disease-free survival is defined as the time from start of RT therapy to date of progression or death due to any cause. If a subject is not known to have progressed or died, then DFS will be censored at the latest date the subject was known to be alive or disease-free (on or before the cut-off date). The DFS distribution will be estimated using the Kaplan-Meier method, and the Kaplan-Meier curves, medians and 95% confidence intervals of the medians will be presented.

Colostomy-free survival distribution will be estimated using the Kaplan-Meier method, and the Kaplan-Meier curves, medians and 95% confidence intervals of the medians will be presented.

OS is defined as the time from start of RT therapy to date of death due to any cause. If a subject is not known to have died, then OS will be censored at the latest date the subject was known to be alive (on or before the study end date). The OS distribution will be estimated using the Kaplan-Meier method, and the Kaplan-Meier curves, medians and 95% confidence intervals of the medians will be presented.

For the HRQOL measures, we will calculate the mean and standard deviations of each of the individual indices at baseline and every 3 months during the duration of the study; we will graphically depict scores at each time point. In addition, we will calculate the difference of the QoL scores at the baseline, time of cCR, and last follow up date and report summary statistics.

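### Local regrowth does not require a prior complete response, so tumour that never cleared in an observed near-complete responder can be counted as regrowth

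*Combined protocol and SAP*

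**What the plan says.** **Who is observed.** Section 4.2.5 says: "If tumor shows near complete response, patient may continue to be observed until the next evaluable timepoint". Section 10.1 defines cCR but gives no criteria for a near-complete response. Section 4.2 divides patients in two at the primary assessment (Time 0). Those not eligible for organ preservation go to TME, and for the rest: "All others will undergo organ preservation and surveillance for local regrowth for 2 years on protocol".

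**Text pointing the other way.** The synopsis says "Those who achieve a clinical complete response will be considered for organ preservation approach", followed by "All other patients will receive standard of care total mesorectal excision (TME". Section 2.3 also describes organ preservation as the management of patients who reach a cCR. Within section 4.2.5, both the surveillance schedule and the work-up of suspected regrowth are worded for patients with a cCR.

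**How regrowth is analysed.** Section 10.2 lists a 2-year rate in which "local regrowth is defined as the presence of adenocarcinoma within the rectal wall or within the mesorectum confirmed by pathology". Section 12.5.1 sets the denominator: "For the secondary outcome of local regrowth rate, the analysis population will include all patients managed with organ preservation approach". Section 12.5.2 gives the estimator: "Local regrowth rate will be calculated as the proportion of patients with local regrowth based on the secondary analysis population". None of these three sections mentions a prior cCR.

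**The concern.** Local regrowth, in the sense of the watch-and-wait series in section 2.2.1, is relapse after a complete response; that section cites 2 of 71 patients. If patients who never had a cCR are in the denominator, and tumour that never cleared is an event, the reported figure mixes two quantities: failure to reach cCR, and relapse after reaching it. It then describes a different group from the primary endpoint's responders and cannot be set beside the cited series.

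The conflict over what happens to a near-complete response adds a second problem. Two analysts with the same data could reasonably report different rates, depending on whether they follow the synopsis or section 4.2. Regrowth is also the only secondary outcome for which section 12.5.1 specifies a separate organ-preservation population.

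**Working it through.** **1. The plan's own figures.** The documents state no expected regrowth rate, so there is none to reproduce. The design that is stated does reproduce. With null cCR 0.2, alternative 0.4, one-sided type I error 0.1 and power 0.9 (section 12.6.2), an exact binomial search gives the optimal Simon design as 17 then 37 patients, stopping at 3 or fewer cCRs and rejecting at 11 or more. Its exact type I error is 0.0948 and its power 0.903. It uses only the cCR count at Time 0, so the regrowth rules do not enter it.

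**2. One patient traced through the rules.** Take a near-complete responder at Time 0 with a positive biopsy at the 3-month visit.

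| Step | Section | Result |
|---|---|---|
| Observed, not resected | 4.2.5 | allowed |
| Group after Time 0 | 4.2 | not sent to TME, so organ preservation and surveillance |
| In the denominator? | 12.5.1 | yes, on that split |
| An event? | 10.2 | yes: adenocarcinoma in the rectal wall, confirmed by pathology |
| Counted? | 12.5.2 | one event in a simple proportion |

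Under the synopsis this patient would have gone to TME at Time 0 and would not be in the regrowth population.

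**3. Effect of each such patient.** Let n be the organ-preservation patients who ever reached cCR, x the regrowths among them, and k the observed patients who never cleared and have pathology-confirmed tumour.

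- Rate after cCR = x/n
- Rate under the current rules = (x + k)/(n + k)
- Excess = k(n − x)/(n(n + k)), positive whenever k > 0 and x < n

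All counts are assumed. The value n = 15 is about 40% of 37, and n = 11 is the rejection threshold.

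| n, x | After cCR | k = 1 | k = 2 |
|---|---|---|---|
| 15, 3 | 3/15 = 20.0% | 4/16 = 25.0% | 5/17 = 29.4% |
| 11, 2 | 2/11 = 18.2% | 3/12 = 25.0% | 4/13 = 30.8% |

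One or two such patients therefore add about 5 to 13 points.

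**4. A wider assumed grid.** Let c be the cCRs at Time 0 (11 or 15), m the near-complete responders observed (3, 5 or 7), f the share of them who never clear (0.5 or 0.8), and r the regrowth after cCR (0.2 or 0.3), with late clearers given the same r.

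- Rate under the current rules = (cr + mf + m(1 − f)r)/(c + m)
- Excess over r = mf(1 − r)/(c + m)

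| r | Lowest (c = 15, m = 3, f = 0.5) | Highest (c = 11, m = 7, f = 0.8) |
|---|---|---|
| 0.2 | (3 + 1.5 + 0.3)/18 = 26.7% | (2.2 + 5.6 + 0.28)/18 = 44.9% |
| 0.3 | (4.5 + 1.5 + 0.45)/18 = 35.8% | (3.3 + 5.6 + 0.42)/18 = 51.8% |

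The excess runs from 1.5 × 0.7/18 = 5.8 points to 5.6 × 0.8/18 = 24.9 points, or about 6 to 25.

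**5. The opposite direction.** If the comparison is with patients in cCR at Time 0 only, and five observed near-complete responders all clear and stay clear, 3/15 = 20% becomes 3/20 = 15%.

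**6. Time at risk.** Follow-up runs from Time 0 and ends after 2 years (section 4.2.5). A patient who first meets the cCR criteria at month 3 has 24 − 3 = 21 months of on-protocol surveillance after the cCR.

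**The case against.** The strongest reply is that the plan, read as a whole, ties organ preservation to cCR. The synopsis, section 2.3 and the surveillance and work-up wording of section 4.2.5 all do so. A near-complete responder is given only a deferral to the next visit and may not yet count as managed with organ preservation. On this view the phrase in section 4.2 is a summary, not a classification rule. This stands in part: the documents do not settle that residual tumour is regrowth, and the classification rests on conflicting text. But none of those passages puts a cCR condition into the definition, denominator or estimator, and this reading leaves observed near-complete responders with no place in the regrowth analysis.

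A reader might infer that the rate is bound to be inflated, and by a large amount. The documents do not support that. The upward shift is certain only for tumour that never cleared and is confirmed by pathology; step 5 shows that late clearers can pull the figure down. The never-clearing shares of 50–80% in step 4 are assumptions. Section 2.2.6 does not support them: it says up to 30% of complete responders are missed at assessment and suggests longer waiting to allow further regression.

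Nor do the documents rank regrowth as a key secondary endpoint, attach a test or threshold to it, or plan a formal comparison with the 2-of-71 series. Error from persistent tumour would make non-operative management look worse, not safer. A rate covering everyone not resected at Time 0 is also a legitimate quantity, provided it is labelled as such.

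**Conclusion.** The point holds as a defect of definition in one secondary endpoint. Sections 10.2, 12.5.1 and 12.5.2 contain no prior-cCR condition, and section 4.2.5 admits patients to observation without one. Following section 4.2, tumour that never cleared is therefore counted as regrowth. The synopsis and section 2.3 conflict with this but do not repair it.

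The direction is firm for persistent, pathology-confirmed tumour. The size is not known. One such patient moves an assumed 20.0% to 25.0%, and the assumed grid gives about 6 to 25 points, but the documents supply no number of near-complete responders, no clearance share and no expected regrowth rate. Precision is low in any case: the exact 95% interval for 3/15 is 4% to 48%. That limits how much a shift of a few points would change the reading, but the figure would still be measuring a mixture. The primary cCR analysis, the sample size and the acceptance criteria in section 12.7 are untouched.

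**What to change.** - **Definition and denominator (10.2, 12.5.1).** Define local regrowth as pathology-confirmed adenocarcinoma in the rectal wall or mesorectum after a cCR documented by the section 10.1 criteria. Take as denominator the patients with a documented cCR who are managed non-operatively.
- **Time origin and estimator (12.5.2).** Record the date on which an observed near-complete responder first meets section 10.1. Estimate the 2-year rate from the cCR date with a method that allows for incomplete follow-up, because late clearers have less than 24 months on protocol. A simple proportion does not do this.
- **Separate reporting.** Report how many near-complete responders were observed, how many later met section 10.1 and how many had persistent disease. State how near-complete response is identified, since section 10.1 does not define it. The rate in all patients not resected at Time 0 can be added as a labelled supplementary figure.
- **Reconciliation.** Make the synopsis and sections 2.3, 4.2 and 4.2.5 agree on how a near-complete response at Time 0 is handled. Which rule applies is a clinical decision for the investigators.
- **Unchanged.** The primary endpoint stays at Time 0.

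The cost is wording, a slightly smaller regrowth denominator and one extra recorded date. That date is not already guaranteed: section 10.1 places the multidisciplinary cCR review at the primary assessment, and the study calendar schedules later examinations but no later cCR determination.

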#### **4.3 General Concomitant Medication and Supportive Care Guidelines**

##### **4.3.1 Supportive care**

Patients should receive routine supportive care while on this study. This includes blood product support, antibiotic treatment, and treatment of other newly diagnosed or concurrent medical conditions.

##### **4.3.2 Antiemetics**

Antiemetics may be used at the discretion of the attending physician.

##### **4.3.3 Blood products**

Blood products are permissible. The use of erythropoietin is strongly discouraged in the adjuvant setting and is not permitted in this trial.

##### **4.3.4 Neulasta and Neupogen**

Neulasta and Neupogen may be used to support maintenance of dose delivery and schedule according to physician discretion.

##### **4.3.5 Diarrhea**

Diarrhea should be managed with loperamide. The recommended dose of loperamide is 4 mg at first onset, followed by 2 mg every 2-4 hours until diarrhea free (maximum 16 mg/day). Use of alternative agents such as Lomotil and tincture of opium is permissible.

#### **4.4 Criteria for Removal from Study**

Patients will receive treatment and follow-up as per Study Calendar until death or end of the study period, whichever occurs first.

A patient has the right to withdraw from the study at any time for any reason without prejudice to his/her future medical care by the physician or at the institution, and the study PI has the right to withdraw a patient from study if they do not follow the treatment recommendations provided by the study investigators.

In the absence of treatment delays, treatment with study agents may span a period of

approximately 4 months (including RT and chemotherapy). Patients may discontinue treatment for any of the following reasons:

- Disease progression,
- Intercurrent illness that prevents further administration of treatment,
- Withdrawal due to patient non-compliance,
- Withdrawal due to patient request,
- Study termination, and/or
- General or specific changes in the patient's condition which render the patient unsuitable for further treatment in the judgment of the investigator or treating physician.

If a patient does not return for a scheduled visit, every effort should be made to contact him/her. In any such circumstance, every effort should be made to document the subject's outcome. Patients who leave Stanford or continue their care elsewhere will be contacted every 6 months by telephone, email, or mail. After three failed attempts to reach the patient, either via mail or telephone or a combination of the two, contact will cease and the patient will be considered lost to follow-up.

#### **4.5 Alternatives**

This study is optional. The alternative is to not participate in the study and receive standard of care treatment which includes TME.

### **5. INVESTIGATIONAL AGENT/DEVICE/PROCEDURE INFORMATION**

No investigational or commercial agents or therapies other than those described may be administered with the intent to treat the patient's malignancy.

### **6. DOSE MODIFICATIONS**

#### **6.1 Chemotherapy**

FOLFOXIRI, mFOLFIRINOX, FOLFOX, XELOX, and 5-FU and capecitabine during radiation are standard regimens that have been widely used for the treatment of colon and rectal cancer for more than a decade. Investigators should refer to package and inserts and local pharmacy practices for a complete list of potential toxicities and adhere to best practices. Treatment interruptions and modifications should be made at the discretion of the treating physician.

Subjects should be assessed for Adverse Events (AEs) once during each chemotherapy cycle, and AEs will be recorded. Serious Adverse Events (SAEs) should be reported promptly as according to the guidelines in this protocol.

Chemotherapy infusion records should be kept in the patient's study chart, either with the Medication Administration Record (MAR) or other clinic records which contain: Date of infusion, dose completed of each agent, modifications if any and reason for modification with supporting source documents as needed. Laboratory results prior to

infusion should also be supplied in the patient study chart, as well as the consultation note if the patient is seen by the treating physician.

Below are recommendations and **not** requirements; **modifications of chemotherapy dose and schedule are allowed as per clinical judgment of patient's treating medical oncologist.**

### 6.1.1 Hematologic Toxicity

- For ANC 1,000/mm^3–1,200/mm^3: Delay chemotherapy until ANC > 1,200/mm^3 then resume chemotherapy at the same dose level.
  - Second or More Occurrence of ANC 1000/mm^3-1200/mm^3: Delay chemotherapy until ANC > 1,200/mm^3 then resume FOLFIRINOX with one dose level reduction for all subsequent cycles. **NOTE:** The dose of leucovorin is not reduced.
- For ANC < 1,000/mm^3: Delay chemotherapy until ANC > 1,200/mm^3, then resume chemotherapy with one dose level reduction for all subsequent cycles. **NOTE:** The dose of leucovorin is not reduced.
- For Febrile Neutropenia (defined as ANC < 1,000/mm^3 and temperature > 100.5°F): Delay chemotherapy until resolution of fever and ANC > 1,200, then resume chemotherapy with one dose level reduction for all subsequent cycles. **NOTE:** The dose of leucovorin is not reduced.
- For Platelets 50,000 K/ul – 75,000 K/ul: Delay chemotherapy until platelets > 75,000 then resume chemotherapy at the same dose level.
  - Second or More Occurrence of platelets 50,000 K/ul - 75,000 K/ul: Delay chemotherapy until platelets > 75,000K/ul, then resume chemotherapy with one dose level reduction for all subsequent cycles. **NOTE:** The dose of leucovorin is not reduced.
- For Platelets < 50,000 K/ul: Delay chemotherapy until recovery to Plts > 75,000 K/ul then resume chemotherapy with one dose level reduction for all subsequent cycles. **NOTE:** The dose of leucovorin is not reduced.

### 6.1.2. Non-Hematologic Toxicity

#### 6.1.2.1 Diarrhea

- For grade 2 Diarrhea (despite optimal medical management):
  - First Occurrence: Delay chemotherapy until recovery to grade  $\leq 1$  or baseline then resume chemotherapy at the same dose level.
  - Second or More Occurrence: Delay chemotherapy until recovery to grade  $\leq 1$  or baseline, then resume chemotherapy with one dose level reduction for all subsequent cycles. **NOTE:** The dose of leucovorin is not reduced.
- For grade 3 Diarrhea (despite optimal medical management):
  - First Occurrence: Delay chemotherapy until recovery to grade  $\leq 1$  or baseline, then resume 5-FU, leucovorin, and oxaliplatin, at the same dose level and irinotecan with one dose level reduction for all subsequent cycles.

- Second or More Occurrence: Delay chemotherapy until recovery to grade  $\leq 1$  or baseline, then resume chemotherapy with one dose level reduction for all subsequent cycles. **NOTE**: The dose of leucovorin is not reduced.
- For grade 4 Diarrhea (despite optimal medical management): Delay chemotherapy until recovery to grade  $\leq 1$  or baseline then resume chemotherapy with one dose level reduction for all subsequent cycles. **NOTE**: The dose of leucovorin is not reduced.

